1. PROTOCOL SYNOPSIS FOR STUDY 201664

Rationale

Objective(s)/Endpoint(s)

Part A: Single ascending dose in healthy volunteers

Objectives	Endpoints
Primary	
Evaluate safety and tolerability of single doses of GSK3039294	Adverse events, laboratory measurements, ECG, vital signs
Secondary	
Evaluate pharmacokinetics of single doses of GSK3039294 and its biotransformation into GSK2315698 (CPHPC)	PK parameters of GSK2315698 and GSK3039294

Part B: Repeat dose in healthy volunteers

[figure not shown]
Objectives	Endpoints
Primary	
Evaluate safety and tolerability of repeat doses of GSK3039294	Adverse events, laboratory measurements, ECG, vital signs and cardiac telemetry (where applicable)
Secondary	
Evaluate pharmacokinetics of repeat doses of GSK3039294 and its biotransformation into GSK2315698 (CPHPC)	PK parameters of GSK2315698 and GSK3039294
Pharmacodynamic effect of repeat doses of GSK3039294 on plasma SAP levels	Plasma SAP levels
Explore correlation of dose of GSK3039294, blood concentration of GSK2315698 and plasma SAP levels	PK parameters of GSK2315698 and GSK3039294 Plasma SAP levels
Exploratory	
Determine the effect of food on a single dose of GSK3039294	PK parameters of GSK2315698 and GSK3039294 under fasted and fed conditions.

Part C: Repeat dose in patients with systemic amyloidosis

Objectives	Endpoints
Primary	
Evaluate safety and tolerability of repeat doses of GSK3039294	Adverse events, laboratory measurements, ECG, vital signs and cardiac telemetry (where applicable).
Secondary	
Evaluate pharmacokinetics of repeat doses of GSK3039294 and its biotransformation into GSK2315698 (CPHPC)	PK parameters of GSK2315698 and GSK3039294
Pharmacodynamic effect of multiple doses of GSK3039294 on plasma SAP levels	Plasma SAP levels and time to repletion of SAP.
Explore correlation of dose of GSK3039294, blood concentration of GSK2315698 and plasma SAP levels	PK parameters of GSK2315698 and GSK3039294 Plasma SAP levels

Overall Design

This is a three-part, open-label, non-randomised study.

Treatment Arms and Duration

Part A: Single dose escalation in healthy volunteers

Two cohorts (cohorts 1 and 2) of subjects will be enrolled to provide data from 6 subjects per cohort and up to 4 different doses (2 dose levels per cohort) of GSK3039294 will be tested.

Subjects will be admitted to the unit on Day -1, following the dose on Day 1 subjects will remain in-house until Day 4. Wash-out will take place from Day 5 to Day 14.

Providing a review of the data from each dose (safety data: AE, vital signs, ECG and laboratory safety test and PK data up to 48 h etc) is favourable, the next dose level will be administered.

Part B: Repeat dose escalation in healthy volunteers

Cohort 3: In a group of healthy volunteers (preferably < 45 years of age) sufficient subjects will be enrolled to ensure 6 completers, the study drug will be administered repeatedly for a total of 7 days. The dose will be one that is expected to be well tolerated based on the single dose data and not predicted to exceed exposure limits based on single dose PK.

A sentinel subject will be dosed first with repeat GSK3039294 administration for 7 consecutive days. Subsequent subjects will only be dosed after the sentinel subject has successfully completed the full 7 days of dosing without any clinically concerning AEs being reported. If the safety data from the sentinel subject is deemed to be equivocal, a second subject can be dosed individually for 7 days at the discretion of the Investigator in consultation with the GSK study team. If the safety data from the second subject is also equivocal, at the discretion of the Investigator in consultation with the GSK study team, subsequent subjects can also be individually dosed with GSK3039294 for 7 days.

The food effect exploration in Cohort 3 will only be conducted once the Investigator in consultation with the GSK study team is satisfied with the safety profile of repeat dose GSK3039294. Following this, the food effect will be conducted on Days 4 and 5, and GSK3039294 will be administered under fasted and then under fed conditions (respectively).

Sufficient subjects will be enrolled to ensure a minimum of 6 subjects complete all study procedures, including the food effect exploration.

Providing a review of the data (safety data: AE, vital signs, ECG, telemetry, laboratory safety tests and PK) is overall acceptable, Cohort 4a will be initiated. The approving REC will be informed of the outcome of this data review.

Cohort 4a: In a group of healthy volunteers sufficient subjects will be enrolled to ensure 6 completers, the study drug will be administered repeatedly for a total of 21 days.

The dose level for this cohort will be determined by a review of the safety and PK data from cohort 3. The dose may be adjusted (up or down) during the 21 day dosing session based on preliminary PK collected during dosing and ongoing review of safety. If the dose is to be altered, this will be done no later than Day 16 in order to achieve a new steady-state at Day 21.

The predicted maximum daily exposure will not exceed pre-clinical safety exposure limits.

Cohort 4b(*optional, only if required*): Based on data from Cohorts 3 and 4a, dose levels may be selected for further investigation in a further cohort of healthy volunteers (recruitment to ensure 6 completers). For this purpose the compound will be dosed for 21 consecutive days. The dose level and / or dosing regimen may be altered once during the 21 days providing a review of the data from the starting dose (safety data: AE, vital signs, ECG, laboratory safety tests and PK – all obtained once steady state has been achieved) is favourable. The predicted maximum daily dose administered will not exceed pre-clinical safety exposure limits.

Part C: Repeat dose escalation in patients with systemic amyloidosis

A single dose level of GSK3039294 will be tested for 21 days repeat dose, in patients with systemic amyloidosis which may include those with cardiac amyloid involvement.

Type and Number of Subjects

In **Part A**, sufficient healthy volunteers will be enrolled to ensure 6 subjects per cohort have completed the in-patient phases.

In **Part B**, sufficient healthy volunteers will be enrolled to ensure 6 subjects per cohort have completed each of the in-patient phases.

In Part A and B of the study, if subjects prematurely discontinue, replacement subjects may be enrolled and assigned to the same cohort at the discretion of the Sponsor in consultation with the investigator. Replacement subjects do not need to have received the first dose for a given cohort to join the study in the second cohort.

In **Part C**, a minimum of 12 patients with systemic amyloidosis will be enrolled. If subjects prematurely discontinue, replacement subjects may be enrolled at the discretion of the Sponsor in consultation with the investigator.

Additional subjects/cohorts may be enrolled to allow for further evaluation of a given dose or for evaluation of additional dose levels.

Analysis

There are no formal hypotheses to be tested as part of this study.

Interim analyses

Safety, PK and PD data will be reviewed on an ongoing basis throughout the study by the study team and investigator in order to inform dosing decisions for subsequent dosing sessions, cohorts and study parts.

In addition, in all Parts of the study, individual profiles over time will also be presented graphically for selected urine and plasma laboratory parameters pertaining to the kidney. To inform dosing decisions for subsequent dosing sessions in Part A, individual values of C_{max} and AUC_[0-inf] will be derived by means of non-compartmental analysis. To inform dosing decisions for subsequent study parts, GSK2315698 concentration data and plasma SAP levels will be analysed using the PK/PD model that was developed for GSK2315698.

Primary and secondary analyses

Safety, PK and PD data will be listed, summarised and presented graphically as appropriate. GSK2315698 concentration data and plasma SAP levels will be analysed using the PK/PD model that was developed for GSK2315698.

Cohort Safety Reviews: A safety review will be performed on completion of each Cohort in Part B, as well as at completion of Cohort 5 in Part C (see Section 4.2.2. & Section 4.2.3.). Initiation of Cohort 4a will be contingent on the findings of the safety review at completion of Cohort 3 (see Section 4.2.2.)

Summary of Cardiac Arrhythmia Adverse Events in Part A of this study

A total of 4 separate arrhythmias in 3 male subjects over 45 year old were reported on 24-hour Holter after single dose administration of GSK3039294 in Part A. Three episodes of supraventricular tachycardia (SVT), all of atrial tachycardia morphology at doses of GSK3039294 at 600mg and 1200mg, and one episode of a single 5-beat accelerated idioventricular rhythm (AIVR) at 600mg GSK3039294, were reported in these 3 separate subjects. Each of the events was of short duration, completely asymptomatic, and was not associated with hemodynamic instability.

No prolongation of the QTcF interval was observed in any subject after administration of 200mg, 600mg, or 1200mg of GSK3039294 in Part A.

Both SVTs and ventricular salvos of short duration are known to occur in healthy volunteer subjects and can be considered to be within the normal (non-pathological) variation of ECG parameters. In this regard, SVTs have been reported to arise in 13.9% of healthy volunteer subjects over 45 years of age compared to an incidence of 1.1% in healthy volunteer subjects 45 years or less in FIH studies (Hingorani et al, 2016). In Part A, none of the three affected subjects had plasma levels of GSK3039294 detectable approximate to the time at which each cardiac arrhythmia occurred. Moreover, the timing

of each of the four arrhythmic events after dosing with GSK3039294 was not associated with the Tmax of CPHPC including one subject whom had no detectable plasma CPHPC present at approximately the time of the first of their two arrhythmic events.

Therefore, at this time, given that there were also no arrhythmogenic liabilities identified for GSK3039294 in preclinical toxicological studies, it is unlikely that the arrhythmias reported after dosing with GSK3039294 in Part A are attributable to its single dose administration at 600 mg or 1200mg.

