4.2.2.1. Sentinel Dosing in Part B

In each individual study cohort in Part B, a sentinel subject will complete all dosing days up to and including Day 7. If there are no clinically concerning safety or tolerability issues observed, the rest of the subjects within the cohort can be dosed.

If the safety data from the sentinel subject is deemed to be equivocal, a second (and subsequent) subjects will complete all dosing days individually, up to and including Day 7, at the discretion of the Investigator in consultation with the GSK study team.

4.2.2.2. 7 Day Repeat Dosing (Cohort 3)

In a group of healthy volunteers, sufficient subjects will be enrolled to ensure a minimum of 6 subjects complete all study procedures (including evaluation of food-effect) associated with 7 days repeat dosing administration. The dose will be one that is expected to be well tolerated based on the single dose data and predicted to not exceed exposure limits based on single dose PK.

A food effect exploration will be conducted at Days 4 and 5 of this cohort once the investigator is satisfied with the safety data from the sentinel subject(s). To evaluate a potential food effect, GSK3039294 will be administered under fasted and then under fed conditions (please see SRM for details of meals), and PK samples will be taken to investigate the food effect on the PK.

Cardiac Safety Review of Cohort 3

Given that all cardiac arrhythmic events after single dose administration of GSK3039294 in Part A (where there were detectable levels of plasma CPHPC) were relatively acute and observed between approximately 4 to 7 hours after t_{max} of CPHPC and when no GSK3039294 was detectable, and given steady state is expected to be reached after approximately 5 days of repeat dosing, 7 day continuous cardiac telemetry in Cohort 3 is deemed to be of sufficient duration to detect any potential cardiac arrhythmias associated with repeat dosing of GSK3039294.

On completion, in addition to full safety review, a cardiac safety review will be performed where individual subject telemetry data will be reviewed in relation to the PK data of GSK3039294 and CPHPC.

4.2.2.3. 21 Day Repeat Dosing (Cohort 4a)

In a group of healthy volunteers sufficient subjects will be enrolled to ensure 6 completers, the study drug will be administered repeatedly for a total of 21 days.

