4.6.3. Overall Benefit:Risk Conclusion

GSK3039294 is an oral prodrug of CPHPC, as such it is expected to release CPHPC after oral administration. Previous clinical experience with CPHPC shows it has a good safety and tolerability profile therefore we do not anticipate safety issues linked to the release of the active moiety.

At this time, although the cardiac arrhythmias reported in Part A are unlikely to be attributable to single dose administration of GSK3039294 at either 600mg or 1200mg, as a precaution, and to further assess and confirm this conclusion, the cardiac safety monitoring of healthy volunteer subjects during repeat dose administration of GSK3039294 for 7 consecutive days in Cohort 3 Part B has been enhanced (see [Section 7.3.7.](#)), and also in systemic amyloidosis patients in Cohort 5 Part C who are known to have cardiac amyloid involvement (see [Section 7.3.8.](#)).

Biotransformation from prodrug into active will release 2 molecules of formaldehyde. There is precedent of licensed prodrugs releasing formaldehyde with no associated toxicity on a background that formaldehyde is physiologically metabolised very rapidly within the systemic circulation ([EFSA Journal, 2014; 12\(2\):3550.](#)).

Preclinical signs of potential nephrotoxicity were observed at very high doses which are unlikely to be reached in the clinic, however monitoring of renal function will be performed in the study in order to detect any potential changes.

There will be no medical benefit to healthy volunteers or patients with systemic amyloidosis being treated with GSK3039294 alone. The design of the study, schedule of assessments, and oversight mean that any risks to participants are minimised including those which might potentially affect the kidney and heart, and therefore the clinical study is justified.

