5.1. Inclusion Criteria

A subject will be eligible for inclusion in this study only if all of the following criteria apply:

All Subjects**[1] AGE**

1. 18 to 70 years of age inclusive at the time of signing the informed consent.

[2] RELEVANT HABITS

1. Non-smokers and Smokers. Smokers (<5 /day) are permitted but must be willing to abstain for the duration of residential study sessions and / or dosing period (whichever is longer).

[3] WEIGHT

1. Body weight > 50kg and body mass index (BMI) \geq 18 kg/m² (inclusive) and excluding the effects of peripheral oedema.

[4] SEX

1. Male or female
2. Female subjects are eligible to participate if they are of non-childbearing potential defined as premenopausal females with a documented tubal ligation or hysterectomy or bilateral oophorectomy; or postmenopausal defined as 12 month of spontaneous amenorrhea (in questionable cases a blood sample with simultaneous follicle stimulating hormone (FSH) > 40 MIU/ml and estradiol < 40 pg/ml (147 pmol/l) is confirmatory
3. Male subjects with female partners of child bearing potential must comply with one of the following contraception requirements from the time of first dose of study medication until completion of the follow-up visit
 - a. Vasectomy with documentation of azoospermia.
 - b. Male condom plus partner use of one of the contraceptive options below:
 - Contraceptive subdermal implant that meets the effectiveness criteria of a <1% rate of failure per year, as stated in the product label
 - Intrauterine device or intrauterine system that meets the SOP effectiveness criteria including a <1% rate of failure per year, as stated in the product label [Hatcher, 2007a]
 - Oral Contraceptive, either combined or progestogen alone [Hatcher, 2007a]
Injectable progestogen [Hatcher, 2007a]
 - Contraceptive vaginal ring [Hatcher, 2007a]
 - Percutaneous contraceptive patches [Hatcher, 2007a]
 - Occlusive cap (female diaphragm or cervical/vault cap) with a vaginal

spermicide (foam, gel, cream or suppository).

These allowed methods of contraception are only effective when used consistently, correctly and in accordance with the product label. The investigator is responsible for ensuring that subjects understand how to properly use these methods of contraception

[5] INFORMED CONSENT

1. Capable of giving signed informed consent as described in Section 10.2 which includes compliance with the requirements and restrictions listed in the consent form and in this protocol

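### Cohort 3 is to confirm that the Part A arrhythmias, all in men over 45, are not drug-related, but the synopsis prefers subjects under 45; a clean result should be claimed only for the ages enrolled.

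*Protocol*

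**What the plan says.** - **Part A events.** The synopsis summary states: "A total of 4 separate arrhythmias in 3 male subjects over 45 year old were reported on 24-hour Holter". Three of the four were atrial tachycardias and one was a five-beat AIVR; all were brief and asymptomatic.
- **Background by age.** The same summary says "SVTs have been reported to arise in 13.9% of healthy volunteer subjects over 45 years of age compared to an incidence of 1.1" per cent at 45 years or less. The title of the cited source in Section 11 shows that these are 24-hour Holter recordings.
- **Task of the monitoring.** Section 4.6.3 judges the Part A events unlikely to be due to single doses of 600 mg or 1200 mg. It says monitoring in Cohort 3, and in Cohort 5 patients with cardiac amyloid, was enhanced "as a precaution, and to further assess and confirm this conclusion".
- **Who is enrolled.** The synopsis prefers Cohort 3 subjects under 45: "In a group of healthy volunteers (preferably < 45 years of age) sufficient subjects will be enrolled to ensure 6 completers". Section 4.2.2.2 does not repeat this, and Section 5.1 sets the age for all subjects as "18 to 70 years of age inclusive at the time of signing the informed consent".
- **Sufficiency.** Section 4.2.2.2 argues from event timing and time to steady state: "7 day continuous cardiac telemetry in Cohort 3 is deemed to be of sufficient duration to detect any potential cardiac arrhythmias". Age is not mentioned.
- **What follows.** Section 4.2.2.3 opens Cohort 4a if the Cohort 3 safety review shows an acceptable profile. No age preference is stated for Cohort 4a.

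**The concern.** The monitoring is asked to settle a question that arose only in men over 45, in a cohort steered towards younger subjects. A quiet cohort of younger subjects is the expected result whether or not the drug provokes arrhythmia in older ones. Nothing requires anyone over 45 to be enrolled, and nothing asks the Cohort 3 review to say which ages its conclusion covers. Followed as written, the plan could report the Part A question as confirmed and open Cohort 4a at 18 to 70 years, with the affected age group largely unexamined on repeat dosing.

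The point is sharper because Cohort 3 is the only healthy-volunteer repeat-dose cohort for which Sections 5.2 and 7.3.5 specify a screening Holter exclusion and detailed telemetry. Section 4.6.1 lists continuous telemetry during in-patient dosing as a general mitigation, but Section 7.3.5 details it only for Cohort 3 and for Cohort 5 patients with cardiac amyloid.

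**Working it through.** **Inputs.** n = 6 completers (Synopsis; 4.2.2.2). Background SVT probability per subject: 0.011 at 45 or less, 0.139 over 45 (Synopsis; 24-hour recordings). Prior Beta(1,1) (Table 11). On-treatment telemetry of about 7 days (4.2.2.2; 7.3.5.1).

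**1. The plan's own precision figure.** With 0 of 6 the posterior is Beta(1,7).
- Lower limit: 1 − 0.975^(1/7) = 0.004.
- Upper limit: 1 − 0.025^(1/7) = 0.410.

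This reproduces Table 11, (0.00, 0.41). A clean cohort leaves true rates up to 41% inside the interval, and the interval describes only the population sampled.

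**2. Chance of a clean cohort from background alone, all six aged 45 or less.**
- 24-hour rate taken as the whole-period rate: (1 − 0.011)^6 = 0.989^6 = 0.936.
- Seven independent days: 0.989^(6×7) = 0.989^42 = 0.63.

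The protocol gives no 7-day rate, so 0.63 to 0.94 is a range set by the assumption about dependence between days. The 48-hour Holter exclusion would raise these values by an amount that the protocol does not give.

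**3. The same cohort if a drug effect existed only above 45.** Every enrolled subject still has the background rate, so the probability is again 0.63 to 0.94. A clean result cannot separate this case from no effect, whichever rate is used.

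**4. The same cohort if the drug multiplied the rate at every age.** The multiples are assumptions; the protocol gives no effect size.

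| Multiple | Rate at ≤45 | Clean, 24-hour rate | Clean, 7 independent days |
|---|---|---|---|
| 2 | 0.022 | 0.978^6 = 0.875 | 0.978^42 = 0.39 |
| 10 | 0.110 | 0.890^6 = 0.497 | 0.890^42 = 0.007 |

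A younger cohort can therefore reveal a large effect that does not depend on age. For a modest one it remains weak.

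**5. What enrolling over-45s would cost in background.** Six subjects, all over 45, before any Holter exclusion: clean with probability 0.861^6 = 0.407 on the 24-hour rate, and 0.861^42 = 0.002 on seven independent days. On the 24-hour rate, the chance of at least one background SVT is 6.4% with none of six over 45, 38.3% with three and 59.3% with six.

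**6. The texts side by side.** The events arose over 45 (Synopsis). The monitoring is to confirm non-attribution (4.6.3). The preferred subjects are under 45 (Synopsis; absent from 4.2.2.2 and 5.1). The next cohort is 18 to 70 (4.2.2.3 with 5.1). No passage limits the conclusion to the ages observed.

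**The case against.** The strongest case is that the preference is deliberate and sensible. The study has no control group, so an event in a low-background cohort is easier to attribute. Step 5 shows that six unselected over-45s could well produce background SVT that nobody could interpret. The preference also keeps first repeat dosing away from the group with the unexplained events. This stands, and it is why the age preference itself is not the error. It helps to interpret a positive result, however; it does not make a clean one confirmatory for over-45s.

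The screening Holter exclusion does not remove the trade-off. No figure in the protocol shows how far it lowers background. Part A also scheduled a 24-hour screening Holter, although its results are not given.

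A reader might infer more than the documents support:

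- **That Cohort 3 says nothing about the affected group.** The preference is not an eligibility bar, and step 4 shows that a large age-independent effect could appear in younger subjects. No passage proposes an effect confined to over-45s; it is an alternative that the design cannot exclude.
- **That the synopsis contradicts the body.** A soft preference is compatible with an 18-to-70 criterion. It is an omission to reconcile.
- **That a clean Cohort 3 opens Part C.** Section 4.2.3 ties Cohort 5 to the Cohort 4 review, and Section 4.2.3.1 adds renal and cardiac sentinels.
- **That telemetry alone opens Cohort 4a.** The review also covers adverse events, vital signs, ECG, laboratory tests and PK. Cohort 4a has its own sentinel, a Day 7 individual review and arrhythmia stopping criteria.

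The Cohort 3 cardiac review relates individual telemetry to drug concentrations and is not an event-count test. Section 4.6.3 also names Cohort 5, but there telemetry covers only patients with cardiac amyloid, after the Cohort 4a decision.

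**Conclusion.** The point holds as a limit on the conclusion. Section 4.6.3 claims a confirmation that a mostly younger cohort cannot give for the age group in which the events arose. If all six are 45 or less, a clean result has probability 0.63 to 0.94 from background alone, and exactly the same if an effect were confined to over-45s. The 41% upper limit for 0 of 6 does not extend to ages that were not enrolled.

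The range assumes the protocol's 24-hour SVT rates, dependence between days anywhere from complete to none, and no adjustment for the Holter exclusion. It covers SVT only; the protocol gives no background rate for AIVR. The weakness shrinks as more over-45s are enrolled. The Part A conclusion concerns single doses and Cohort 3 tests repeat dosing, which is a further reason for modest wording.

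**What to change.** Reconcile the Cohort 3 description in the synopsis, Sections 4.2.2.2 and 4.6.3, and the age criterion in 5.1, so that they say the same thing about whom Cohort 3 is meant to include.

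Then change Section 4.6.3 and the Cohort 3 cardiac safety review in Section 4.2.2.2 so that:

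1. telemetry findings are reported by age, with the number of subjects aged 45 or less and over 45;
2. the conclusion on attribution is limited to the ages studied;
3. if few or none over 45 were enrolled, the review says that attribution in that group remains unresolved, and this is before those who decide on Cohort 4a.

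Whether to keep the age preference is for the sponsor: it lowers background and so aids attribution of an event, at the price of information about over-45s. If it is kept, its reason should be stated in Section 4.2.2.2.

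The cost is wording and one extra column in the review listing. No added subjects or assessments are needed.
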